9 DESIGN

9.1 Study Design

The intratumoral efficacy of the combination of Interferon Alpha-2b, rintatolimod, and celecoxib will be evaluated by administering fixed doses of each drug. Subjects will receive 3 weeks of the Chemokine Modulation (CKM) regimen, administered on days 1, 2, 3, 8, 9, 10, 15, 16, and 17 of protocol treatment, according to the safe established dosing levels (see Table 1). During this time, subjects will be monitored continuously for safety, based on Bayesian analysis.

Table 1 Dosing

[figure not shown]
Components of the chemokine modulation regimen		
Interferon Alpha-2b (20 million units/M ²) IV over 20 minutes once a day for 3 consecutive days, repeated weekly over 3 weeks (days 1,2,3,8,9,10,15,16,17).	Rintatolimod (200 mg) IV once a day for 3 consecutive days, repeated weekly over 3 weeks (days 1,2,3,8,9,10,15,16,17). Initial administration should begin at a slow rate of infusion (approximately 20 cc/ hour). Increase rate to 40cc/hour after 30 minutes.	Celecoxib (200 mg, orally, twice a day) for 3 consecutive days, repeated weekly over 3 weeks (days 1,2,3,8,9,10,15,16,17). Doses should be given approximately 12 hours apart.

PROTOCOL TITLE: Phase 2A Study Evaluating a Chemokine-Modulatory Regimen in Patients with Colorectal Cancer Metastatic to the Liver

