11.1.1 Screening (performed between days -14 through day -1 unless otherwise specified)

- Recording of concomitant medications
- Medical and Surgical History
- Complete Physical Exam including height and weight
- Vital Signs
- ECOG Performance Status Assessment
- Hematology
- Chemistry
- CEA Level
- ANA testing
- Serum HCG pregnancy testing (within 7 days of Day 1 in women of child-bearing potential only)
- CT and/or MRI (within 28 days of start of treatment)
- EKG
- Liver Biopsy

11.1.2 Evaluations Performed on day 1 of each treatment week (day 1, 8, 15):

- Recording of concomitant medications
- Recording of Adverse Events
- Targeted Physical Exam including weight
- Vital Signs (temperature, blood pressure, pulse rate and respiratory rate) will be performed pre- treatment and at 30 and 60 minutes post rintatolimod
(± 5 minutes).
- ECOG Performance Status Assessment
- Hematology
- Chemistry
- Chemokine Modulating regimen
- Blood (60cc) for correlative studies on Day 1 and Day 15 only (within 1 hour after end of infusion treatment)

PROTOCOL TITLE: Phase 2A Study Evaluating a Chemokine-Modulatory Regimen in Patients with Colorectal Cancer Metastatic to the Liver

11.1.3 Evaluations Performed on days 2 and 3 of each treatment week(days 2,3, 9, 10, 16, 17):

- Recording of concomitant medications
- Recording of Adverse Events
- Vital Signs (temperature, blood pressure, pulse rate and respiratory rate) will be performed pre-treatment and at 30 and 60 minutes post rintatolimod (\pm 5 minutes).
- Chemokine Modulating regimen
- Blood (60cc) for correlative studies on Day 3 only (within 1 hour after end of infusion treatment)

11.1.4 Evaluations Performed on Day 20 (+/- 2 days):

- Recording of Adverse Events
- Liver Biopsy

11.1.5 End of Treatment Visit on Day 29 (+/- 10 days):

- Recording of concomitant medications
- Recording of Adverse Events
- Targeted Physical Exam including weight
- Vital Signs
- ECOG Performance Status
- Hematology
- Chemistry

NOTE: In the event patient cannot tolerate treatment with all 9 days of treatment, then Blood 60cc for correlative will be collected at time that the patient recovers from toxicities (ideally within 1 week of the last infusion). Liver biopsy will also be collected provided there is not an overriding safety concern for the patient.

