- **Reporting Adverse Events:** Routine AEs occurring between the start date of intervention until 30 days after the last intervention, or until the event has resolved, the study participant is lost to follow-up, the start of a new treatment, or until the study investigator assesses the event(s) as stable or irreversible, will be reported. New information will be reported after it is received.

Table 2 Guidelines for Routine Adverse Event Reporting (Regardless of Expectedness)

Attribution	Grade 1	Grade 2	Grade 3	Grade 4
Unrelated			X	X
Unlikely			X	X
Possible	X	X	X	X
Probable	X	X	X	X
Definite	X	X	X	X

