17.3 Serious Adverse Events

A serious adverse event (SAE) is any adverse event (experience) that in the opinion of either the investigator or sponsor results in **ANY** of the following:

- Death.
- A life-threatening adverse event (experience). Any AE that places a participant or participants, in the view of the Investigator or sponsor, at immediate risk of death from the reaction as it occurred. It does NOT include an AE that, had it occurred in a more severe form, might have caused death.
- Inpatient hospitalization or prolongation of existing hospitalization (for > 24 hours).
- A persistent or significant incapacity or substantial disruption of the ability to conduct normal life functions.
- A congenital anomaly or birth defect.
- Important Medical Event (IME) that, based upon medical judgment, may jeopardize the participant and may require medical or surgical intervention to prevent one of the outcomes listed above.

Reporting Serious Adverse Events

All new SAEs occurring from the date the participant signs the study consent until 30 days after the last intervention or a new treatment is started, whichever comes first, will be reported. The RPCI SAE Source Form is to be completed with all available information, including a brief narrative describing the SAE and any other relevant information.

PROTOCOL TITLE: Phase 2A Study Evaluating a Chemokine-Modulatory Regimen in Patients with Colorectal Cancer Metastatic to the Liver

SAEs occurring after the 30 day follow-up period that the investigator determines to be possibly, probably or definitely related to the study intervention should be reported.

SAEs identified as an Unanticipated Problem by the Investigator must be reported. Please refer to Section 17.5 for details on reporting Unanticipated Problems.

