19.4 Safety Monitoring

Safety Evaluation: A previous Phase I study utilized the same dosing strength (at a different dosing schedule: 5 days versus the proposed 3 days), but only gave one cycle; whereas the current study purposes 3 consecutive weeks of 3-day treatments. As such, a continuous toxicity monitoring plan will be implemented to quickly identify the emergence of any new AEs or SAEs.

Subject safety will be monitored continuously using Bayesian methods with the following decision rule: if the posterior probability is .80 or greater than 33% or more of treated subjects experience a treatment related serious adverse event (SAE), then the study will be suspended pending review. This posterior probability will be calculated from the study's accumulating data and a weakly informative prior distribution. If π denotes a random variable representing the proportion of subjects who will experience a treatment related SAE, we assume π has a beta distribution with parameters $a = 1$ and $b = 2$.

Selected values of the posterior distribution $PP(\pi \geq .33 | \text{SAEs and prior})$ are shown in the table below. Also shown are the binomial probabilities of suspending the study for observed count of SAE's.

Table X Number of Subjects Observed to Have Treatment-Related SAEs and Corresponding Posterior and Binomial Probabilities Needed to Suspend the Study

Subjects	Treatment-Related SAEs	$PP(\pi > 33\%)^*$	$Pr(X \geq r p = .33)$
2	2	.892	.109
3	3	.956	.036
4	3	.903	.108
5	3	.832	.205
6	4	.915	.097
7	4	.860	.168
8	5	.927	.085
9	5	.883	.140
10	5	.829	.206

PROTOCOL TITLE: Phase 2A Study Evaluating a Chemokine-Modulatory Regimen in Patients with Colorectal Cancer Metastatic to the Liver

11	6	.901	.117
12	6	.857	.171
13	6	.805	.233
14	7	.880	.143
15	7	.836	.195

* π is the SAE rate. The minimum acceptable upper bound of a treatment-related SAE is 33%. PP($\pi > 33\%$) is the posterior probability that the SAE rate exceeds this 33% upper bound. This posterior probability of an SAE is calculated from the prior distribution, the number of subjects treated and the observed number of treatment-related SAEs.

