It is anticipated that 15 patients will be enrolled to this study. The table above presents the minimum number of subjects experiencing treatment-related SAEs (i.e., those SAEs judged to be possibly, probably, or definitely related to the study regimen) that would dictate suspension of the trial in accordance with the stopping rule. Using these assumptions the trial will be suspended if:

- 2 subjects experience treatment related SAE among the first 2 subjects enrolled
- 3 subjects experience treatment related SAE among 3 – 5 subjects or,
- 4 subjects experience treatment related SAE among 6 – 7 subjects or,
- 5 subjects experience treatment related SAE among 8 – 10 subjects or,
- 6 subjects experience treatment related SAE among 11 – 12 subjects,
- 7 subjects experience treatment related SAE among 13 – 15 subjects.
- Any death not clearly due to the underlying disease or extraneous causes

At the completion of the study, all AEs will be summarized by weekly treatments and grade using frequencies and relative frequencies.

Treatment Related SAEs for Safety Monitoring

Treatment Related SAEs will be defined as the following events that occur during the period of Day 1 through the End of Treatment visit:

- \geq Grade 3 treatment-related non-hematologic toxicities, except:
 - The following grade \geq 3 toxicities (lasting <7 days)
Flu-like symptoms/constitutional symptoms (i.e., fever, chills, arthralgias, myalgias)
Depression, anxiety, restlessness, or insomnia
GI symptoms (i.e., nausea, diarrhea)
AST/ALT (unless accompanied by Grade 2 increased bilirubin)
 - Please note, if the above grade 3 toxicities last ≥ 7 days, they will be defined as a DLT
- \geq Grade 4 treatment related non-hematologic toxicity
- Hy's law criteria:

PROTOCOL TITLE: Phase 2A Study Evaluating a Chemokine-Modulatory Regimen in Patients with Colorectal Cancer Metastatic to the Liver

- An elevated alanine transaminase (ALT) or aspartate transaminase (AST) lab value that is greater than or equal to three times (3X) the upper limit of normal (ULN) and
- An elevated total bilirubin lab value that is greater than or equal to two times (2X) ULN and, at the same time, an alkaline phosphatase (ALP) lab value that is less than 2X ULN,
- As a result of within-protocol-specific testing or, unscheduled testing

Safety Review and Study Suspension

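### The suspension rule stops counting events at an End of Treatment visit that may fall 2 to 22 days after the last dose, while related events are reported for 30 days

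*Combined protocol and SAP*

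**What the plan says.** **Counting window (19.4).** "Treatment Related SAEs will be defined as the following events that occur during the period of Day 1 through the End of Treatment visit". Listed grade 3 toxicities that last less than 7 days are excepted.

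**End of Treatment visit (11.1.5; same timing in Appendix F).** "End of Treatment Visit on Day 29 (+/- 10 days". The visit is stated as a study day. No section sets a minimum interval between the last dose and this visit.

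**Dosing (9.1).** The regimen is "administered on days 1, 2, 3, 8, 9, 10, 15, 16, and 17 of protocol treatment". Section 10.1.1 allows treatment to be delayed by up to 3 weeks. The documents do not say whether the End of Treatment visit then moves.

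**Reporting windows.** Section 17.2 covers "Routine AEs occurring between the start date of intervention until 30 days after the last intervention" and also lists other end points, such as resolution or the start of new treatment. Section 17.3 collects new SAEs "until 30 days after the last intervention or a new treatment is started, whichever comes first, will be reported". It keeps a route open for "SAEs occurring after the 30 day follow-up period that the investigator determines to be possibly, probably or definitely related to the study intervention".

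**Decision rule (19.4).** The study is suspended "if the posterior probability is .80 or greater than 33% or more of treated subjects experience a treatment related serious adverse event (SAE"). The prior is Beta(1, 2), and Table X gives the limits for 2 to 15 subjects.

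**The concern.** Section 19.4 introduces continuous monitoring because the earlier phase I study gave a single cycle, whereas this study gives three weekly ones. Toxicity that appears after the third course is therefore of direct interest to the rule. Yet that is where the count is cut off, at a point set by visit scheduling rather than by the actual last dose.

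Two consequences follow. First, a related qualifying event between the End of Treatment visit and the end of the reporting window is recorded but leaves the posterior unchanged, so suspension becomes less likely at any given true rate. Second, the posterior treats each subject as one equal yes/no observation, although one subject may be watched for 2 days after the last dose and another for 22.

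**Working it through.** **1. Reproduce Table X.** With r events in n subjects and a Beta(1, 2) prior, the posterior is Beta(1 + r, 2 + n − r), and the rule uses its upper tail at 0.33.
- n = 15, r = 7: Beta(8, 10) gives 0.836; the binomial tail at 0.33 is 0.195. Both match the table.
- All 14 rows reproduce to three decimals in both columns, and each tabulated r is the smallest that reaches 0.80.

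**2. Length of the counting window, on-schedule dosing.**
- Visit range: 29 − 10 = Day 19; 29 + 10 = Day 39.
- Days after the last dose: 19 − 17 = 2; 29 − 17 = 12; 39 − 17 = 22.
- End of 30-day reporting: 17 + 30 = Day 47.
- Reportable days outside the count: 47 − 19 = 28; 47 − 29 = 18; 47 − 39 = 8.

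**3. What one uncounted event can do.** At n = 15, seven events give 0.836 and suspend the study. If one of the seven falls after the End of Treatment visit, six are counted: Beta(7, 11) gives 0.685 and the study continues.

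**4. Effect on the chance of suspension.** Let p be the true per-subject rate of qualifying related events, and m the share of subjects with such an event whose first one falls after the End of Treatment visit. The counted rate is p(1 − m). The probability of ever reaching a Table X limit was computed exactly, one subject at a time, for n = 2 to 15. The documents give no value for m, so a range is shown as an assumption.

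| m | p = 0.40: counted rate | P(suspend) | p = 0.50: counted rate | P(suspend) |
|---|---|---|---|---|
| 0% | 0.400 | 0.58 | 0.500 | 0.81 |
| 2% | 0.392 | 0.55 | 0.490 | 0.79 |
| 5% | 0.380 | 0.52 | 0.475 | 0.76 |
| 10% | 0.360 | 0.46 | 0.450 | 0.71 |
| 20% | 0.320 | 0.36 | 0.400 | 0.58 |

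**5. Sensitivity.** The bullet list in 19.4 requires 7 events at 13 subjects where Table X gives 6. Using 7 there lowers each probability by less than 0.02.

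**The case against.** **Day 19 is the early edge.** A reader might infer that counting normally ends two days after the last dose. The documents do not support that: the nominal visit is Day 29, 12 days after the last dose, and Appendix F lists the biopsy visit (Day 20 ± 2) before it. What stands is that Day 19 is permitted, and that even at Day 29, 18 of the 30 days are uncounted.

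**Events that need 7 days.** A reader might infer that a listed grade 3 toxicity starting in the third course can never count, because its 7 days cannot be complete by Day 19. Section 19.4 does not require that. It counts events that occur in the window and can be read as counting by onset, with the event added once its duration is known. This needs clarifying, no more.

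**A shorter monitoring window is not a contradiction.** This is correct. No section says that the rule must run for 30 days, so 19.4 does not conflict with 17.2 or 17.3. The weakness is a window of variable length, without a stated reason and not tied to the actual last dose.

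**Late events are not unmonitored.** This also stands. SAE and unanticipated-problem reporting, FDA reports, DSMC and early-phase committee review, and the trigger for deaths not clearly due to disease (which has no stated window) all remain. They do not feed the quantitative rule.

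**Much of the expected toxicity is early.** The background sections mainly describe flu-like and infusion-related effects, so m may be small. Nothing in the documents supports 10% or 20%; at 2% the loss is about 0.02.

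**Conclusion.** The point holds in a limited form. Followed as written, 19.4 omits related qualifying events that the study already reports, and it closes each subject's count 2 to 22 days after an on-schedule last dose (12 nominally) while the model treats subjects as equally observed.

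The day arithmetic is certain for on-schedule dosing. The effect on the rule is not, because it depends on an unknown m. Over 2% to 20%, the probability of suspension drops by about 0.02 to 0.22 at a true rate of 40% (0.58 to between 0.55 and 0.36) and by about 0.02 to 0.24 at 50% (0.81 to between 0.79 and 0.58). These figures assume independent subjects, Table X limits and a count updated after every subject. They should not be read as a finding that the rule loses a fifth of its events.

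This is a cheap improvement to the study's quantitative safety rule, not an error in Table X.

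**What to change.** In 19.4, define the count as qualifying related events with onset from Day 1 through 30 days after the actual last dose, or to the start of new treatment if that is earlier. This matches the AE and SAE reporting windows in 17.2 and 17.3. State that a duration-based event is added when it reaches 7 days. The prior, the threshold and Table X stay as they are.

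The cost is a wording change, with two limits to acknowledge:
- Each subject's count stays open longer, so some totals will be updated after later subjects have enrolled. Observation would still end early for subjects who start new treatment.
- A reader might infer that all the needed data are already collected. Related AEs and SAEs are reportable, but scheduled hematology and chemistry end at the End of Treatment visit, and the footnote on the Day 46 adverse-event entry in Appendix F describes survival follow-up. Laboratory-based events after that visit, including Hy's law cases, would be found only through unscheduled testing, which 19.4 already accepts as a source for Hy's law.

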20 PROVISIONS TO MONITOR THE DATA TO ENSURE THE SAFETY OF SUBJECTS

This study will be reviewed at the scheduled RPCI Early Phase Clinical Trials (EPCT) meetings and the minutes are forwarded to the IRB for review.

21 VULNERABLE POPULATIONS

- N/A

22 COMMUNITY-BASED PARTICIPATORY RESEARCH

- N/A

23 SHARING OF RESULTS WITH SUBJECTS

Individual response data is shared with the participant as a part of their clinical care.

24 SETTING

Potential subjects with recurrent colorectal cancer will be identified and recruited during scheduled visits to the RPCI Gastrointestinal Center. Potential subjects, who are referred by their RPCI or community physicians, will be scheduled with an investigator in the clinic for evaluation. All participants related research procedures will be conducted at RPCI.

25 PROVISIONS TO PROTECT THE PRIVACY INTERESTS OF SUBJECTS

Any data, specimens, forms, reports, video recordings, and other records that leave the site will be identified only by a participant identification number (Participant ID, PID) to maintain confidentiality. All records will be kept in a limited access environment. All computer entry and networking programs will be done using PIDs only. Information will not be released without written authorization of the participant.

PROTOCOL TITLE: Phase 2A Study Evaluating a Chemokine-Modulatory Regimen in Patients with Colorectal Cancer Metastatic to the Liver

26 RESOURCES AVAILABLE

- N/A

27 PRIOR APPROVALS

- N/A

28 COMPENSATION FOR RESEARCH-RELATED INJURY

Refer to informed consent document related to this study.

29 ECONOMIC BURDEN TO SUBJECTS

Refer to informed consent document related to this study.

30 CONSENT PROCESS

This study will not be initiated until the protocol and informed consent document(s) have been reviewed and approved by a properly constituted Institutional Review Board (IRB) or Independent Ethics Committee (IEC). Each participant (or legal guardian) shall read, understand, and sign an instrument of informed consent prior to performance of any study-specific procedure. It is the responsibility of the investigator to ensure that the participant is made aware of the investigational nature of the treatment and that informed consent is given.

The Investigator is responsible for the retention of the participant log and participant records; although personal information may be reviewed by authorized persons, that information will be treated as strictly confidential and will not be made publicly available. The investigator is also responsible for obtaining participant authorization to access medical records and other applicable study specific information according to Health Insurance Portability and Accountability Act regulations (where applicable).

This study will be conducted in compliance with all applicable laws and regulations of the state and/or country and institution where the participant is treated. The clinical trial should be conducted in accordance with the ethical principles embodied in the Belmont Report: Ethical Principles and Guidelines for the Protection of Human Subjects of Research, consistent with good clinical practice and the applicable regulatory requirements and according to the guidelines in this protocol, including attached appendices.

Informed consent will be obtained according to SOP: Informed Consent Process for Research (HRP-090).

31 PROCESS TO DOCUMENT CONSENT IN WRITING

The Investigator (or IRB specified designee) is responsible for obtaining written consent from each participant or the participant's legally authorized representative in accordance with GCP guidelines using the approved informed consent form, before any study specific procedures (including screening procedures) are performed. The informed consent form acknowledges all information that must be given to the participant according to applicable GCP guidelines, including the purpose and nature of the study, the expected efficacy and possible side effects of the treatment(s), and specifying that refusal to participate will not influence further options for therapy. Any additional information that is applicable to the study must also be included. Additional national or

PROTOCOL TITLE: Phase 2A Study Evaluating a Chemokine-Modulatory Regimen in Patients with Colorectal Cancer Metastatic to the Liver

institutionally mandated requirements for informed consent must also be adhered to. The participant should also be made aware that by signing the consent form, processing of sensitive clinical trial data and transfer to other countries for further processing is allowed.

The Investigator shall provide a copy of the signed consent form to the participant and the signed original shall be maintained in the Investigator File. A copy of the signed consent form must be filed in the participant file. At any stage, the participant may withdraw from the study and such a decision will not affect any further treatment options.

SOP: Written Documentation of Consent (HRP-091) will be followed.

32 DRUGS OR DEVICES

RPCI will hold the IND for this study.

32.1 Celecoxib

A sulfa non-steroidal anti-inflammatory drug (NSAID) used in the treatment of osteoarthritis, rheumatoid arthritis, acute pain, painful menstruation and menstrual symptoms, and to reduce numbers of colon and rectum polyps in patients with familial adenomatous polyposis.

